6.4.2. Full Analysis Population

The full analysis (FA) population will consist of all subjects who received any study product (including control) and for whom immunogenicity endpoint data are available. In the case of mis-randomization subjects will be analyzed according to the study product actually received. Separate populations for each assay and/or dose may be needed if the availability of a sample's data varies across assay or if a subject is only eligible for analyses for one of the doses. For sake of simplicity, immunogenicity tables and figures will use a single "Full Analysis Population" label, however special cases and/or considerations for exclusions from assay- or dose-specific summaries will be provided in footnotes.

6.4.3. Per Protocol Population

The per protocol (PP) population will consist of all subjects who received both doses of study vaccine, for whom immunogenicity endpoint data are available, and who did not have major protocol deviations, such as receipt of non-study vaccines during the time frame prohibited by the protocol or receipt of the second study vaccination substantially out of window. As with the FA population, immunogenicity tables and figures will use a single "Per Protocol Population" label, however special cases and/or considerations for exclusions from assay- or dose-specific summaries will be provided in footnotes.

6.5. Covariates and Subgroups

The protocol does not define any formal subgroup analyses (e.g., analysis based on age, sex, race/ethnicity or other demographic characteristics), and the study is not adequately powered to perform subgroup analyses.

6.6. Missing Data

Missing safety and/or immunogenicity data will not be imputed. No search for outliers will be performed. However, the logarithmic transform will be used as appropriate to improve the distributional properties of the immunogenicity data and reduce the impact of potential outliers.

6.7. Multiple Comparisons/Multiplicity

Since this is a Phase 1 study, the analyses are descriptive and so, neither formal testing nor any adjustments for multiple testing are planned. Since the early analyses of the primary and secondary outcomes are being performed for the sole purpose of planning other/future studies and will not impact the operations of this trial, no adjustments for early testing are planned.

7. STUDY SUBJECTS

7.1. Subject Disposition

A summary of subject screen failures will be presented ([Table 1](#)).

The composition of analysis populations, including reasons for subject exclusion, by treatment arm, will be presented ([Table 2](#)).

The disposition of subjects in the study will be tabulated by treatment group ([Table 3](#)). The table shows the total number of subjects screened, enrolled, receiving at least 1 dose, receiving at least 2 doses, discontinued dosing or terminated from study follow-up prior to the end of the study.

A flowchart showing the disposition of study subjects, adapted from the Consort Statement [1] will be included ([Figure 1](#)). This figure will present the number of subjects screened, enrolled, lost to follow-up, and analyzed, by treatment arm.

7.2. Protocol Deviations

A summary of protocol deviations will be presented by the reason for the deviation, the deviation category, and treatment group for all subjects ([Table 4](#)).

7.3. Demographic and Other Baseline Characteristics

Summaries of categorical and continuous demographics and baseline characteristics will be presented by treatment group ([Table 5](#) and [Table 6](#)) and a demographic listing for all subjects will be presented ([Listing 1](#)). Ethnicity is categorized as Hispanic or Latino, or not Hispanic and not Latino. In accordance with NIH reporting policy, subjects may self-designate as belonging to more than one race or may refuse to identify a race, the latter reflected in the CRF as “No” to each racial option.

7.3.1. Concurrent Illnesses and Medical Conditions

All current illnesses and past pre-existing medical conditions will be MedDRA coded using MedDRA dictionary version 24.1 or higher. Summaries of subjects' pre-existing medical conditions will be presented by treatment group ([Table 7](#)).

7.3.2. Prior and Concurrent Medications

Summaries of medications that were started prior to dosing and continuing at the time of dosing will be presented by WHO Drug Terms 1 and 2 and treatment group ([Table 8](#)).

7.4. Measurements of Treatment Compliance

All subjects are intended to receive two doses of study product administered in the clinic. The dates of treatment by vaccination and treatment group will be provided ([Listing 2](#)). The number of subjects receiving one or two doses will be summarized in the previously described disposition table ([Table 3](#)).

8. SAFETY EVALUATION

The analyses of safety data will be primarily descriptive. Data will be represented to show difference in reactogenicity signs and symptoms and adverse events between the vaccine candidate and dose groups. Grading scales are provided in the clinical protocol.

8.1. Adverse Events

When calculating the incidence of adverse events (i.e., on a per subject basis), each subject will only be counted once and any repetitions of adverse events within a subject will be ignored; the denominator will be the total population size. All adverse events reported will be included in the summaries and analyses.

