6. GENERAL STATISTICAL CONSIDERATIONS

6.1. General Principles

All continuous variables will be summarized using the following descriptive statistics: n (non-missing sample size), mean, standard deviation, median, maximum and minimum. The frequency and percentages (based on the non-missing sample size) of observed levels will be reported for all categorical measures. In general, all data will be listed, sorted by treatment and subject, and when appropriate by visit number within subject. All summary tables will be structured with a column for each treatment (HydroVax-002 YFV, Placebo) and will be annotated with the total population size relevant to that table/treatment, including any missing observations.

Multiple observations within specific visit period are accepted. In the case of multiple observations within a specific window, the assessment value that is closest to the scheduled visit window will be used in the analyses for the post-baseline records. For screening and baseline visits, the last assessment value will be used. All the recorded data will be listed. If observations have the same distance to the scheduled assessment, the latest one will be used.

SAS version 9.4 or above will be used to generate all tables, figures, and listings.

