Blood And Blood Forming Organs	Any Level 2 Codes	x	x.x	x	x.x	x	x.x	x	x.x
	Antianemic Preparations	x	x.x	x	x.x	x	x.x	x	x.x
	Antithrombotic Agents	x	x.x	x	x.x	x	x.x	x	x.x
Cardiovascular System	Any Level 2 Codes	x	x.x	x	x.x	x	x.x	x	x.x
	Diuretics	x	x.x	x	x.x	x	x.x	x	x.x
Dermatologicals	Any Level 2 Codes	x	x.x	x	x.x	x	x.x	x	x.x
	Antibiotics And Chemotherapeutics For Dermatological Use	x	x.x	x	x.x	x	x.x	x	x.x
	Antifungals For Dermatological Use	x	x.x	x	x.x	x	x.x	x	x.x
	Antipruritics, Incl. Antihistamines, Anesthetics, Etc.	x	x.x	x	x.x	x	x.x	x	x.x
	Corticosteroids, Dermatological Preparations	x	x.x	x	x.x	x	x.x	x	x.x
	Emollients And Protectives	x	x.x	x	x.x	x	x.x	x	x.x

		HydroVax-002 YFV 1 mcg (N=XX)		HydroVax-002 YFV 5 mcg (N=XX)		Placebo (N=XX)		All Subjects (N=XX)	
WHO Drug Code Level 1, Anatomic Group	WHO Drug Code Level 2, Therapeutic Group	n	%	n	%	n	%	n	%
	Other Dermatological Preparations	x	x.x	x	x.x	x	x.x	x	x.x
Genito Urinary System And Sex Hormones	Any Level 2 Codes	x	x.x	x	x.x	x	x.x	x	x.x
	Other Gynecologicals	x	x.x	x	x.x	x	x.x	x	x.x
	Sex Hormones And Modulators Of The Genital System	x	x.x	x	x.x	x	x.x	x	x.x
	Urologicals	x	x.x	x	x.x	x	x.x	x	x.x
Musculo-Skeletal System	Any Level 2 Codes	x	x.x	x	x.x	x	x.x	x	x.x
	Antiinflammatory And Antirheumatic Products	x	x.x	x	x.x	x	x.x	x	x.x
Nervous System	Any Level 2 Codes	x	x.x	x	x.x	x	x.x	x	x.x
	Analgesics	x	x.x	x	x.x	x	x.x	x	x.x
	Antiepileptics	x	x.x	x	x.x	x	x.x	x	x.x
	Psychoanaleptics	x	x.x	x	x.x	x	x.x	x	x.x
	Psycholeptics	x	x.x	x	x.x	x	x.x	x	x.x
Respiratory System	Any Level 2 Codes	x	x.x	x	x.x	x	x.x	x	x.x
	Antihistamines For Systemic Use	x	x.x	x	x.x	x	x.x	x	x.x
	Cough And Cold Preparations	x	x.x	x	x.x	x	x.x	x	x.x
	Drugs For Obstructive Airway Diseases	x	x.x	x	x.x	x	x.x	x	x.x
	Nasal Preparations	x	x.x	x	x.x	x	x.x	x	x.x
Sensory Organs	Any Level 2 Codes	x	x.x	x	x.x	x	x.x	x	x.x
	Ophthalmologicals	x	x.x	x	x.x	x	x.x	x	x.x
Various	Any Level 2 Codes	x	x.x	x	x.x	x	x.x	x	x.x
	General Nutrients	x	x.x	x	x.x	x	x.x	x	x.x
	Unspecified Herbal And Traditional Medicine	x	x.x	x	x.x	x	x.x	x	x.x

N = Number of subjects in the Safety population.

n = Number of subjects reporting taking at least one medication in the specific WHO Drug Class

Table 9: Summary of Adverse Events – Safety Population

Subjects ^a with	HydroVax-002 YFV		HydroVax-002 YFV		Placebo (N = xx)	
	1 mcg (N = xx)	%	5 mcg (N = xx)	%	n	%
At least one local solicited adverse event	x	x	x	x	x	x
At least one systemic solicited adverse event	x	x	x	x	x	x

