At least one unsolicited adverse event	x	x	x	x	x	x
At least one related unsolicited adverse event	x	x	x	x	x	x
Mild (Grade 1)	x	x	x	x	x	x
Moderate (Grade 2)	x	x	x	x	x	x
Severe (Grade 3)	x	x	x	x	x	x
At least one severe (Grade 3) unsolicited adverse event	x	x	x	x	x	x
Related	x	x	x	x	x	x
Unrelated	x	x	x	x	x	x
At least one laboratory toxicity	x	x	x	x	x	x
At least one related laboratory toxicity	x	x	x	x	x	x
Mild (Grade 1)	x	x	x	x	x	x
Moderate (Grade 2)	x	x	x	x	x	x
Severe (Grade 3)	x	x	x	x	x	x
At least one severe (Grade 3) laboratory toxicity	x	x	x	x	x	x
Related	x	x	x	x	x	x
Unrelated	x	x	x	x	x	x
At least one serious adverse event ^b	x	x	x	x	x	x
At least one related, serious adverse event	x	x	x	x	x	x
At least one adverse event leading to early termination ^c	x	x	x	x	x	x

N = Number of subjects in the Safety Population and is the denominator for percentages

a: Subjects are counted once for each main category (i.e., non-indented row) regardless of the number of events. Subjects may be counted in more than one main category.

b: A listing of Serious Adverse Events is included in the Serious Adverse Event Listing.

c: As reported on the Adverse Event eCRF.

Table 10: Subject-Level Summary of Solicited Events by Symptom, Severity, Dose, and Treatment Group – Safety Population

Symptom	Severity	Post-Dose 1						Post-Dose 2						Post-Either Dose															
		HydroVax-002 YFV 1 mcg (N = xx)			HydroVax-002 YFV 5 mcg (N = xx)			Placebo (N = xx)			HydroVax-002 YFV 1 mcg (N = xx)			HydroVax-002 YFV 5 mcg (N = xx)			Placebo (N = xx)			HydroVax-002 YFV 1 mcg (N = xx)			HydroVax-002 YFV 5 mcg (N = xx)			Placebo (N = xx)			
		n	%	95% CI	n	%	95% CI	n	%	95% CI	n	%	95% CI	n	%	95% CI	n	%	95% CI	n	%	95% CI	n	%	95% CI	n	%	95% CI	
Any Symptom																													
Any Symptom	None	x	xx	x.x, x.x	x	xx	x.x, x.x	x	xx	x.x, x.x	x	xx	x.x, x.x	x	xx	x.x, x.x	x	xx	x.x, x.x	x	xx	x.x, x.x	x	xx	x.x, x.x	x	xx	x.x, x.x	
	Any Severity																												
	Mild																												
	Moderate																												
	Severe																												
Any Systemic Symptom																													
[Systemic Symptom 1]	None																												
	Any Severity																												
	Mild																												
	Moderate																												
	Severe																												
[Systemic Symptom 2]	None																												
	Any Severity																												
	Mild																												
	Moderate																												

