	Severe																												

Symptom	Severity	Post-Dose 1						Post-Dose 2						Post-Either Dose														
		HydroVax-002 YFV 1 mcg (N = xx)			HydroVax-002 YFV 5 mcg (N = xx)			Placebo (N = xx)			HydroVax-002 YFV 1 mcg (N = xx)			HydroVax-002 YFV 5 mcg (N = xx)			Placebo (N = xx)			HydroVax-002 YFV 1 mcg (N = xx)			HydroVax-002 YFV 5 mcg (N = xx)			Placebo (N = xx)		
		n	%	95% CI	n	%	95% CI	n	%	95% CI	n	%	95% CI	n	%	95% CI	n	%	95% CI	n	%	95% CI	n	%	95% CI	n	%	95% CI
Any Local Symptom																												
[Local Symptom 1]	None																											
	Any Severity																											
	Mild																											
	Moderate																											
	Severe																											
[Local Symptom 2]	None																											
	Any Severity																											
	Mild																											
	Moderate																											
	Severe																											

N = Number of subjects in the Safety Population with solicited event data available for the specified time period and is the denominators for percentages.

The Any Symptom counts classify each subject by the maximum severity reported for the category; each subject is only counted once.

Table 11: Number and Percentage of Subjects Experiencing Systemic Solicited Events by Symptom, Severity, Day Post Dosing, and Treatment Group – Post-Dose 1 – HydroVax-002 YFV, 1 mcg

HydroVax-002 YFV - 1 mcg, N=XX													
		Post-Vac		Day 1		Day 2		Day 3		Day 4		Day 5-7	
Symptom	Severity	n	%	n	%	n	%	n	%	n	%	n	%
Any Systemic Symptoms	None	x	x.x	x	x.x	x	x.x	x	x.x	x	x.x	x	x.x
	Mild	x	x.x	x	x.x	x	x.x	x	x.x	x	x.x	x	x.x
	Moderate	x	x.x	x	x.x	x	x.x	x	x.x	x	x.x	x	x.x
	Severe	x	x.x	x	x.x	x	x.x	x	x.x	x	x.x	x	x.x
	Not Reported	x	x.x	x	x.x	x	x.x	x	x.x	x	x.x	x	x.x
Elevated Oral Temperature	None	x	x.x	x	x.x	x	x.x	x	x.x	x	x.x	x	x.x
	Mild	x	x.x	x	x.x	x	x.x	x	x.x	x	x.x	x	x.x
	Moderate	x	x.x	x	x.x	x	x.x	x	x.x	x	x.x	x	x.x
	Severe	x	x.x	x	x.x	x	x.x	x	x.x	x	x.x	x	x.x
	Not Reported	x	x.x	x	x.x	x	x.x	x	x.x	x	x.x	x	x.x
Feverishness	None	x	x.x	x	x.x	x	x.x	x	x.x	x	x.x	x	x.x
	Mild	x	x.x	x	x.x	x	x.x	x	x.x	x	x.x	x	x.x
	Moderate	x	x.x	x	x.x	x	x.x	x	x.x	x	x.x	x	x.x
	Severe	x	x.x	x	x.x	x	x.x	x	x.x	x	x.x	x	x.x
	Not Reported	x	x.x	x	x.x	x	x.x	x	x.x	x	x.x	x	x.x
Fatigue	None	x	x.x	x	x.x	x	x.x	x	x.x	x	x.x	x	x.x
	Mild	x	x.x	x	x.x	x	x.x	x	x.x	x	x.x	x	x.x
	Moderate	x	x.x	x	x.x	x	x.x	x	x.x	x	x.x	x	x.x
	Severe	x	x.x	x	x.x	x	x.x	x	x.x	x	x.x	x	x.x
	Not Reported	x	x.x	x	x.x	x	x.x	x	x.x	x	x.x	x	x.x

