Symptom	Severity	Post-Vac		Day 1		Day 2		Day 3		Day 4		Day 5-7	
		n	%	n	%	n	%	n	%	n	%	n	%
Any Local Symptoms	None	x	x.x	x	x.x	x	x.x	x	x.x	x	x.x	x	x.x
	Mild	x	x.x	x	x.x	x	x.x	x	x.x	x	x.x	x	x.x
	Moderate	x	x.x	x	x.x	x	x.x	x	x.x	x	x.x	x	x.x
	Severe	x	x.x	x	x.x	x	x.x	x	x.x	x	x.x	x	x.x
	Not Reported	x	x.x	x	x.x	x	x.x	x	x.x	x	x.x	x	x.x
Pain at injection site	None	x	x.x	x	x.x	x	x.x	x	x.x	x	x.x	x	x.x
	Mild	x	x.x	x	x.x	x	x.x	x	x.x	x	x.x	x	x.x
	Moderate	x	x.x	x	x.x	x	x.x	x	x.x	x	x.x	x	x.x
	Severe	x	x.x	x	x.x	x	x.x	x	x.x	x	x.x	x	x.x
	Not Reported	x	x.x	x	x.x	x	x.x	x	x.x	x	x.x	x	x.x
Tenderness	None	x	x.x	x	x.x	x	x.x	x	x.x	x	x.x	x	x.x
	Mild	x	x.x	x	x.x	x	x.x	x	x.x	x	x.x	x	x.x
	Moderate	x	x.x	x	x.x	x	x.x	x	x.x	x	x.x	x	x.x
	Severe	x	x.x	x	x.x	x	x.x	x	x.x	x	x.x	x	x.x
	Not Reported	x	x.x	x	x.x	x	x.x	x	x.x	x	x.x	x	x.x
Induration/Swelling Measurement	None	x	x.x	x	x.x	x	x.x	x	x.x	x	x.x	x	x.x
	Mild	x	x.x	x	x.x	x	x.x	x	x.x	x	x.x	x	x.x
	Moderate	x	x.x	x	x.x	x	x.x	x	x.x	x	x.x	x	x.x
	Severe	x	x.x	x	x.x	x	x.x	x	x.x	x	x.x	x	x.x
	Not Reported	x	x.x	x	x.x	x	x.x	x	x.x	x	x.x	x	x.x

Placebo, N=XX													
		Post-Vac		Day 1		Day 2		Day 3		Day 4		Day 5-7	
Symptom	Severity	n	%	n	%	n	%	n	%	n	%	n	%
Erythema/Redness Measurement	None	X	X.X	X	X.X	X	X.X	X	X.X	X	X.X	X	X.X
	Mild	X	X.X	X	X.X	X	X.X	X	X.X	X	X.X	X	X.X
	Moderate	X	X.X	X	X.X	X	X.X	X	X.X	X	X.X	X	X.X
	Severe	X	X.X	X	X.X	X	X.X	X	X.X	X	X.X	X	X.X
	Not Reported	X	X.X	X	X.X	X	X.X	X	X.X	X	X.X	X	X.X
Induration/Swelling (functional grade)	None	X	X.X	X	X.X	X	X.X	X	X.X	X	X.X	X	X.X
	Mild	X	X.X	X	X.X	X	X.X	X	X.X	X	X.X	X	X.X
	Moderate	X	X.X	X	X.X	X	X.X	X	X.X	X	X.X	X	X.X
	Severe	X	X.X	X	X.X	X	X.X	X	X.X	X	X.X	X	X.X
	Not Reported	X	X.X	X	X.X	X	X.X	X	X.X	X	X.X	X	X.X

N = Number of subjects in the Safety Analysis Population who received the specified dose. Severity is the maximum severity reported post dosing for each subject for each day or interval.

Table 23: Unsolicited Adverse Events by MedDRA System Organ Class and Preferred Term, Severity, and Treatment Group – Safety Population

MedDRA System Organ Class	MedDRA Preferred Term	Severity	HydroVax-002 YFV 1 mcg (N = xx)				HydroVax-002 YFV 5 mcg (N = xx)				Placebo (N = xx)			
			n	%	95% CI	m	n	%	95% CI	m	n	%	95% CI	m
Any SOC	Any PT	Any Severity	x	xx	xx, xx	xx	x	xx	xx, xx	xx	x	xx	xx, xx	xx
		Mild	x	xx	xx, xx	xx	x	xx	xx, xx	xx	x	xx	xx, xx	xx
		Moderate	x	xx	xx, xx	xx	x	xx	xx, xx	xx	x	xx	xx, xx	xx
		Severe	x	xx	xx, xx	xx	x	xx	xx, xx	xx	x	xx	xx, xx	xx

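### SAP 8.1 and Table 9 divide solicited events by the whole Safety Population while SAP 6.1 and Table 10 divide by subjects with data, so Table 9 can understate reactogenicity when a dosed subject has no solicited data

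*SAP*

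**What the plan says.** Occurrence of solicited local events and occurrence of solicited systemic events, each over the 7 days after each vaccination, are two of the six primary outcome measures (SAP 3.2; protocol section 3). The SAP gives these denominators:

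- **SAP 8.1**, on counting each subject once: "any repetitions of adverse events within a subject will be ignored; the denominator will be the total population size". The sentence stands above both 8.1.1 (solicited) and 8.1.2 (unsolicited), so it covers both.
- **Table 9 footnote**: "N = Number of subjects in the Safety Population and is the denominator for percentages". The first rows of that table are solicited, beginning with "At least one local solicited adverse event". They pool the two doses and have no confidence interval and no row for missing data.
- **Table 10 footnote**: "Number of subjects in the Safety Population with solicited event data available for the specified time period and is the denominators for percentages". The periods are post-dose 1, post-dose 2 and post-either dose, each with a 95% CI.
- **SAP 6.1**: "The frequency and percentages (based on the non-missing sample size) of observed levels will be reported for all categorical measures".
- **SAP 6.6**: "Missing safety and/or immunogenicity data will not be imputed".

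Tables 11 to 22 show severity by day, with a Not Reported row for each symptom. The footnote printed under Table 22 reads "N = Number of subjects in the Safety Analysis Population who received the specified dose".

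SAP 8.1.1 grades each solicited symptom from 0 (absent) to 3. It has them recorded 30 minutes after vaccination and then daily for 7 days.

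**The concern.** For unsolicited events, dividing by everyone exposed is conventional, because the absence of a report is itself the observation. Solicited events differ. Here absence is a grade that someone has to record, so a dosed subject with no solicited record has not been observed to be free of reactions. Under the SAP 8.1 rule that subject still enters the denominator and is counted as event-free, and nothing in Table 9 shows it. Under the SAP 6.1 and Table 10 rule the subject is left out.

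The groups have 10, 10 and 5 subjects, so one subject is worth 10 or 20 percentage points. Dosed subjects are not replaced (protocol 7.2.2), and most of the daily record comes from a memory aid that the subject completes (protocol 8.5.1.1). At stake is an overview table that may show a lower reaction rate than the detailed table for the same primary endpoint. No SAP text says which of the two is the primary estimate.

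**Working it through.** **Inputs.** N is the number of dosed subjects in a group: 10, 10 and 5 (SAP section 5). x is the number with at least one recorded solicited event after either dose. m is the number of dosed subjects with no solicited data after either dose. The documents give no value for m or x, so m = 0, 1 or 2 and the values of x are assumptions.

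**The plan's own figures.** The exact two-sided upper 95% limit for 0/10 is 1 − 0.025^(1/10) = 30.85%, against the stated 30.8%. The chance of at least one event at a true rate of 15% is 1 − 0.85^10 = 80.3%, as stated. Both reproduce, so Clopper-Pearson limits are used below.

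**Like with like.** The solicited rows of Table 9 pool the doses, so their counterpart is Table 10 Post-Either Dose.

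- Table 9 rate = x/N
- Table 10 rate = x/(N − m)
- Gap = x/(N − m) − x/N = xm/[N(N − m)]
- Rate that complete data would give: between x/N (no missing subject had an event) and (x + m)/N (all of them did)

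**One subject without data (m = 1).** With N = 10 the gap is x/90: 1/90 = 1.1 points for one event, 9/90 = 10.0 points for nine. With N = 5 it is x/20: 1/20 = 5.0 points for one event, 4/20 = 20.0 points for four.

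| N | m | x | Table 9 | Table 10 (95% CI) | Gap, points | Possible complete-data rate |
|---|---|---|---|---|---|---|
| 10 | 0 | 4 | 40.0% | 40.0% (12.2 to 73.8) | 0.0 | 40.0% |
| 10 | 1 | 0 | 0.0% | 0.0% (0 to 33.6) | 0.0 | 0.0 to 10.0% |
| 10 | 1 | 1 | 10.0% | 11.1% (0.3 to 48.2) | 1.1 | 10.0 to 20.0% |
| 10 | 1 | 4 | 40.0% | 44.4% (13.7 to 78.8) | 4.4 | 40.0 to 50.0% |
| 10 | 1 | 9 | 90.0% | 100.0% (66.4 to 100) | 10.0 | 90.0 to 100.0% |
| 10 | 2 | 4 | 40.0% | 50.0% (15.7 to 84.3) | 10.0 | 40.0 to 60.0% |
| 5 | 1 | 1 | 20.0% | 25.0% (0.6 to 80.6) | 5.0 | 20.0 to 40.0% |
| 5 | 1 | 4 | 80.0% | 100.0% (39.8 to 100) | 20.0 | 80.0 to 100.0% |

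In every row the Table 9 rate equals the lower end of the last column. It can therefore be too low but not too high. With m = 0 the tables agree. With x = 0 both show 0%, and only the exact upper limit moves, from 30.8% on 10 to 33.6% on 9.

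**Which subjects count toward m.** This depends on what qualifies as available solicited data, and the SAP does not say. If a clean 30-minute clinic record qualifies, a subject with nothing afterwards stays in Table 10 as None. Tables 9 and 10 then agree, and both may be too low for a 7-day endpoint.

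**The case against.** The case on the other side is substantial.

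- **An unreturned diary is not the same as no solicited data.** A reader might infer that any dosed subject without a diary drops out of Table 10. The documents do not support that. There is a 30-minute record after each dose, the memory aid is reviewed on Days 2, 4 and 8 after each dose, and the injection site is evaluated on Days 4 and 15 (protocol 1.2). Complete absence of solicited data should be uncommon. This stands.
- **A diary missing after one dose only makes no gap.** A subject with data after the other dose stays in the Post-Either Dose denominator. This stands. Only the dose-specific columns of Table 10 lose the subject.
- **Table 9 need not be wrong.** A reader might infer that it does understate. That holds only if the missing subject in fact had an event. If not, Table 9 is right and Table 10 is too high. This stands, so the claim is that Table 9 can understate.
- **Tables 11 to 22 are not a third rival rate.** They show severity by day and display missing records openly. Their footnote appears only under Table 22, so extending it to all twelve tables is an inference. This stands.
- **The primary estimate can be identified.** Protocol 9.4.2 asks for exact confidence intervals, and among the solicited tables only Table 10 has a CI column. SAP 8.1.1 presents Table 9 as a summary of recorded events, so a breach of the no-imputation rule in SAP 6.6 is a matter of interpretation. This is fair, but it does not remove the conflict: SAP 8.1 states a general rule for incidence that SAP 6.1 and Table 10 do not follow.

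**Conclusion.** The concern holds in a limited form. The SAP states two denominators for solicited events and does not reconcile them, and the SAP 8.1 rule counts a dosed subject with no solicited record as free of events.

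A numerical difference arises only if at least one dosed subject has no qualifying solicited data after either dose and at least one event occurs in that group. On the assumption of exactly one such subject, Table 9 is below Table 10 Post-Either Dose by 1.1 to 10.0 points for 1 to 9 events in a vaccine group of 10, and by 5.0 to 20.0 points for 1 to 4 events in placebo. With none, the gap is zero. The missing counts are assumptions throughout. The documents do not show that such missingness will occur, or that subjects with reactions are the ones more likely to be missing.

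The direction is firm: taking recorded events as correct, Table 9 sits at the bottom of the possible range.

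**What to change.** Make four changes before the unblinded analysis:

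1. In SAP 8.1, limit the sentence on the total population size to unsolicited AEs and SAEs.
2. In the solicited rows of Table 9, use the Table 10 denominator: subjects with solicited data for the stated period, which for these pooled rows is post-either dose.
3. Define the minimum data. A 30-minute post-vaccination record alone does not count as solicited data for the 7-day period unless it records an event. Without this, a clean clinic record would still score an otherwise unobserved subject as event-free.
4. Print the number with no data in each column of Tables 9 and 10. A reader can then compute both limits, x/N and (x + m)/N. This matters because the revised rate can itself be too high if the missing subjects had no events.

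The cost is about one sentence and one footnote, with no new data. When data are missing, rates will be slightly higher and intervals wider. When none are missing, nothing changes.
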